Harnessing the Power of Technology: MOMBA for Postpartum Smoking NCT02237898

09/07/2017

Overview: Through a pilot, randomized control trial tested the effectiveness of Momba Live Long (the Momba Live Long application and sensor) on 7-day point prevalence of smoking abstinence rates i) at the end of the trial and ii) at 3-month follow-up as determined by the Timeline Follow Back instrument and number of negative breath tests.

The randomized controlled trial of Momba Live Long utilized a control group which received financial incentives at an in-person office/clinic visit based on expired CO levels obtained through the piCO+TM CO sensor compared to the MoMba Livelong application. We used results from frequently administered assessment instruments over the course of an 3-month period and subsequent 6- and 12-month follow ups to assess outcomes and to examine the reliability and validity of assessment measures, and key methodological parameters, such as effect size, proportion of eligible and willing study participants, attrition rate, time necessary for data collection, and necessary skill sets for CMHAs. The RCT involved an intervention arm (10 women who receive Momba Live Long) and "control" arm (10 women who receive financial incentives delivered in-person in the office). Participants were randomized using a number generation mechanism provided to the CMHAs who are screening and enrolling women.

Intervention Group (Momba Live Long): The intervention group received a smartphone, data plan, Momba Live Long, including the Bluetooth enabled CO sensor, and training from a CMHA on its use. The intervention group did most of its CO tests remotely, outside of a baseline, 3-month end point assessment, and 6-month and 12-month follow-ups. However, participants also came n for the first 5 days of week 1 to be trained on how to use the Sensordrone and Momba Live Long app. As part of this training, we showed the intervention group participants a Demonstration Video and a Powerpoint Presentation about how to use the Momba Live Long Application. Intervention group participants came to the office for a visit in Week 4 and Week 8 to calibrate the Sensordrone and to submit a urine specimen.

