Control Group: Control group mothers received traditional, in-office contingency management to prevent smoking relapse. Financial incentives were delivered according to the same schedule at the same frequency as those delivered to mothers on Momba Live Long. The exception was that mothers in Momba Live Long will also receive payment for completing tasks that promote abstinence. Overall, the amount of Contingency Management incentives in the two groups were similar. Thus, we were not directly comparing the effectiveness of contingency management that has already been well established, but rather we assess the effectiveness of contingency management delivered over a smartphone application vs. traditional contingency management in an office setting. Women in each condition were provided with the Staying Smoke Free curriculum. Mothers in the control condition completed the same assessment battery and according to the same schedule as participants in the Momba Live Long application group and were compensated similarly. During the first 3 months, control group participants completed assessments with staff during office visits. In months 4-12, surveys were administered via Qualtrics links on personal smartphones, over the phone with research staff, or by mailing the surveys to and from participants' homes. Control group CM breath tests were conducted with the piCO+TM, considered as "traditional" Contingency Management. They also completed Sensordrone CO tests for comparison purposes with the Intervention Group. Control participants were also be compensated for attending each scheduled CO test office visit.

Participants: Women who were smoking in the second or third trimester of pregnancy, with no complicating general medical or psychiatric conditions (including other substance use disorder) were eligible. Women were not receiving other smoking cessation medication. Mothers were not eligible to participate if they were planning to move out of the New Haven area in the next 15 months after study enrollment, had medical complications that would interfere with testing the Sensordrone, or were actively suicidal, psychotic or unable to provide informed consent.

Screening and Enrollment: We used rolling enrollment (over a

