2-month period) and women were followed up to 15 months after study start date. Following a brief description of the study by the Community Mental Health Ambassadors (CMHAs), mothers who live in New Haven and have been trained as research assistants, at a woman's prenatal visit at YNHH or at a community hub visit, women were screened in person or over the phone for smoking status using the Fagerstrom Test for Nicotine Dependence (FTND), a sixitem self-report form that gives a quantitative measure of the severity of nicotine dependence.(37) The study screening form collected personal contact information and significant other contact information as well as demographics and health history. An abbreviated version of the Mental Test Score (33) was used to determine any cognitive impairment or inability to provide informed consent. The CMHAs performed a brief in-person or phone screening, a more complete in-office screening for those still eligible (including submitting a urine specimen to confirm pregnancy and cotinine and to exclude other drug use), and obtained written informed consent.

The screening consent also included a Release of Information (ROI) from YNHH and other local medical providers to obtain medical records about pregnancy and smoking status, pregnancy complications and medical exclusion criteria. These records were reviewed to confirm medical conditions which may interfere with the results of the Sensordrone. A second Release of Information was completed with the consent to participate requesting information about pregnancy and delivery status.

All women were approached until the target enrollment has been reached.

Delivery of the Momba Live Long Intervention: After completion of screening, consents and intake interview, women were provided with a smartphone and data plan, a carbon monoxide sensor compatible with their phone, access to the Momba Live Long application, and training on its use by the CMHAs. This exchange of equipment and training occurred at our office at the end of week 1 of study start date. Testing of CM lasted 12 weeks.

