In office monitoring: Women were required to come into the office to perform in-person CO breath tests using the Sensorcon SensordroneTM and Bedfont piCO+TM in order for us to continue to compare data on the reliability and validity of the Sensordrone. At each office visit women completed additional questionnaires and urine tests to measure cotinine levels to provide additional data on the validity of the SensordroneTM and other drug use (to see if these other drugs affect how well the Sensordrone performs).

Financial incentives were delivered based on the CO breath test. We followed standard protocols for in office monitoring of smoking abstinence and the delivery of financial incentives in

[figure not shown]
pregnant and postpartum women. These included the provision to all participants of the Smoke Free curriculum in addition to the financial incentives to promote abstinence. We required women to report to our clinical office for 5 consecutive days for abstinence monitoring the first week of study enrollment. The frequency of in-office abstinence monitoring decreased to twice weekly in week 2. Frequency of visits in weeks 3-12 depended on accuracy of the Sensordrone; at most, in weeks 3-8 it was twice per week and in weeks 9-12 it was once per week. In-office visits for breath tests were not required after week 12.

Administration of Standardized Measures: All follow-up measures, with the exception of baseline, post, and 6-month post CM and 12-month post CM follow-ups (administered in-office by research assistants, and mostly on a laptop computer) were administered via the Momba Live Long application. Mothers were prompted by the Momba Live Long application upon login and push notifications, to complete the questionnaires at specified intervals. The outcome measures we assessed were: (1) acceptability of the smartphone application to low-income, pregnant women (as defined by the percentage of women who would recommend the site to a friend); (2) point and 7-day smoking prevalence as determined by the Timeline Follow Back assessment, and # of negative breath tests, (secondary outcome); and (3) correlation coefficients between the piCO+TM and the Sensordrone TM specific to expired CO measurement and verified through urine cotinine levels.

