The Phen-X was used to generate diagnoses of depression, anxiety disorders (including trauma and stress disorders), and substance use disorders at baseline and 6-month follow-up. We will collect detailed information about enrolled mothers from the eligibility screening interview and baseline and outcome assessments. Specific instruments utilized and delivered via the Momba Live Long application and the in-person office visits included:

Smoking cessation outcome assessments- In addition to the results of the CO monitor (which only can detect nicotine levels up to 2 to 3 hours after a cigarette), urine will be tested in the office with a qualitative cotinine cassette test from Redwood Toxicology Laboratory and sent to the Dept. Laboratory Medicine, at Yale School of Medicine for confirmation and cotinine levels. Other drugs tested in the office using cassette and dip tests from Redwood Toxicology Laboratory will be for amphetamines, barbiturates, benzodiazepines, cocaine, methadone, Methamphetamine, opiates, PCP, THC and Oxycodone.Self-report of cigarette smoking history was collected with the timeline follow-back (TLFB) for the past 28 days. Measures at post, 6M post CM and 12M post CM included the Fagerstrom Test for Nicotine Dependence, and the self-report of cigarette smoking history using the timeline follow-back (TLFB) for the past 28 days.

Proposed Analytic Plan: The goal of the proposed analysis is to determine the feasibility of the web-based intervention and acceptability and perceived value of the Momba Live Long smartphone-based system. We will evaluate progress toward these goals looking specifically at: (1) ensuring a process exists to assess best practices and participant opinion and integrate them into Momba Live Long and (2) ensuring procedures exist to support and monitor intervention delivery and dissemination.

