For the RCT dependent variables are the 7-day point prevalence of smoking abstinence rates i) at the end of the trial and ii) at 3-month follow-up. We will also compare 2-week continuous smoking abstinence rates at these time points. Smokers are considered abstinent based on self-reported smoking abstinence verified by CO levels <6 ppm and self-report abstinence based on the Timeline Follow Back. (50) Because abstinence is categorical, a binary random effects logit model will be used. (51) As a secondary analysis, we will add an indicator variable for intensity of utilization for Momba Live Long application to the model in order to determine if it contributes significantly to response. Given that this is a pilot, we are not powered

to detect a significant difference on our outcomes. However, we will develop effect sizes to estimate power for a larger study and we will evaluate the direction and consistency of effects. We use guidelines for Stage 1b studies, which suggest 15-30 participants per cell. (52) For the outcome of 7-day point prevalence for smoking abstinence at the end of the trial, and 15 subjects per condition, a 2-tailed alpha of .05 we will have power of 90% if we have the same effect size found in other studies of contingency management with perinatal women smokers. (34) In all likelihood, the effect will be smaller for the 3-month outcomes. However, these results will provide a reasonable estimate with which to power a larger study.

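### The 90% power is stated for 15 women per arm, the trial is described with 10, and the effect size behind the figure is not given

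*Combined protocol and SAP*

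**What the plan says.** The overview at the start of the combined protocol and SAP gives the size of both arms: "The RCT involved an intervention arm (10 women who receive Momba Live Long") and a control "arm (10 women who receive financial incentives delivered in-person in the office"). That is 20 women. It also says the trial is meant to examine "key methodological parameters, such as effect size, proportion of eligible and willing study participants, attrition rate", among other things.

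The last paragraph of Data Analysis for Pilot RCT uses a different number. It follows a Stage 1b guideline of 15 to 30 participants per cell. For 7-day point-prevalence abstinence at the end of the trial it then states: "15 subjects per condition, a 2-tailed alpha of .05 we will have power of 90% if we have the same effect size" as in other contingency management studies of perinatal smokers. It gives a reference, but no abstinence rates, difference, odds ratio or test. The same paragraph says that the pilot is not powered to detect a difference and that its results will be used to power a larger study.

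Three other places bear on the point:

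- Screening and Enrollment refers to a target without giving its number: "All women were approached until the target enrollment has been reached".
- Control Group says of the two arms: "Overall, the amount of Contingency Management incentives in the two groups were similar". The app arm is also paid for completing tasks that promote abstinence.
- Proposed Analytic Plan says "The goal of the proposed analysis is to determine the" feasibility and acceptability of the intervention.

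**The concern.** The plan's only power figure belongs to a trial of 30 women, and the trial described has 20. A reader cannot tell whether 15 was the target and 10 the number reached, or whether one of the two is an error. The 90% does not describe a comparison with 10 per arm.

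Nor can the figure be checked at 15 per arm, because it depends on an effect size that is not stated. Both arms receive contingency management and differ mainly in how it is delivered, so the size of the difference that 90% power requires is itself of interest.

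What is at stake is how the result is used later. The pilot estimate is meant to inform a larger trial. Whoever plans that trial needs the true number per arm and the precision it gives.

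**Working it through.** **Inputs from the document.** Two-sided alpha 0.05, power 90% and 15 per condition (Data Analysis for Pilot RCT); 10 per arm (overview); a binary outcome, abstinent or not.

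**Inputs assumed.** The lower-arm abstinence rate p1 is not given, so a range is used. The test behind the 90% is not named, so three two-proportion tests at a single time point are used. The planned analysis is a random effects logit model, which these tests only approximate.

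**Step 1: the plan's own figure.** It cannot be reproduced without an effect size. It can only be solved backwards, for the effect that gives 90% at 15 per arm.

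**Step 2: arcsine approximation.** With h = 2·asin(√p2) − 2·asin(√p1), the required effect is

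h = (1.960 + 1.282)/√(15/2) = 3.242/2.739 = 1.184.

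Power for the same effect at 10 per arm is

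Φ(h·√(10/2) − 1.960) = Φ(1.184 × 2.236 − 1.960) = Φ(0.687) = 0.754.

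**Step 3: exact enumeration.** For Fisher's exact test and the uncorrected chi-square test, power is the sum of Bin(a; n, p1) × Bin(b; n, p2) over all tables (a, b) that the test rejects. For each p1, p2 was solved so that the test itself has 90% power at n = 15. Power was then recalculated at n = 10. The difference between arms is p2 − p1.

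| p1 | Arcsine p2 | Chi-square p2 | Chi-square power, n = 10 | Fisher p2 | Fisher power, n = 10 |
|---|---|---|---|---|---|
| 2% | 0.448 | 0.456 | 0.658 | 0.530 | 0.606 |
| 5% | 0.532 | 0.526 | 0.675 | 0.613 | 0.658 |
| 10% | 0.627 | 0.622 | 0.698 | 0.705 | 0.677 |
| 20% | 0.757 | 0.760 | 0.737 | 0.820 | 0.678 |
| 30% | 0.849 | 0.850 | 0.726 | 0.904 | 0.677 |
| 40% | 0.916 | 0.912 | 0.691 | 0.955 | 0.652 |
| 50% | 0.963 | 0.962 | 0.672 | 0.989 | 0.576 |

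For p1 from 5% to 40%, power at 10 per arm is 75% (arcsine), 68% to 74% (chi-square) or 65% to 68% (Fisher). The exact powers fall towards both ends of the table. At p1 = 0.1% they are 60% (chi-square) and 54% (Fisher).

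The difference needed for 90% at 15 per arm, for p1 from 5% to 40%, is 48 to 56 points (arcsine and chi-square) or 56 to 62 points (Fisher). For example, at p1 = 20% the Fisher difference is 0.820 − 0.200 = 0.620. At p1 = 2% it is 43 points (arcsine), 44 (chi-square) or 51 (Fisher). At p1 = 50% it is 46 to 49 points.

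**Step 4: precision.** Newcombe's 95% interval for a difference combines the Wilson limits (l, u) of each rate:

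lower = d − √[(p1 − l1)² + (u2 − p2)²], upper = d + √[(u1 − p1)² + (p2 − l2)²], with d = p1 − p2.

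Here p1 and p2 are the two observed rates. With equal rates in both arms the half-widths are:

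| Rate in both arms | 10 per arm | 15 per arm |
|---|---|---|
| 10% | 0.32 | 0.25 |
| 30% | 0.36 | 0.30 |
| 50% | 0.37 | 0.32 |

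The 15-per-arm column uses fractional counts (1.5, 4.5, 7.5).

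Example at 10 per arm: 6/10 against 3/10 abstinent, d = 0.30. The Wilson limits are 0.313 to 0.832 and 0.108 to 0.603.

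Lower = 0.30 − √[(0.600 − 0.313)² + (0.603 − 0.300)²] = −0.12.

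Upper = 0.30 + √[(0.832 − 0.600)² + (0.300 − 0.108)²] = 0.60.

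The interval runs from −12 to +60 points.

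**The case against.** The strongest reply is that nothing depends on the 90%. The plan calls the trial an unpowered pilot just before giving the figure, and makes the figure conditional on an assumed effect. The stated goal is feasibility and acceptability, and the numerical criteria for that (60% participation, 80% retention) do not use power. This stands and keeps the point modest. It does not remove it, because the same paragraph claims 90% power and intends the estimate for planning a larger study. The label "and # of negative breath tests, (secondary outcome") may also show that smoking prevalence is secondary, but it could apply to the breath tests alone.

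A second reply is that 15 is planning text left in a document otherwise written after the event: the overview is mostly in the past tense, the analysis section in the future. That is plausible, but no sentence says so. If it is right, a power figure recalculated for the achieved number adds little, and deleting the sentence is the cleaner course.

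Third, the effect size comes from a cited source not available here. The 90% is therefore unverifiable rather than shown to be wrong at 15 per arm, and nothing is claimed about the comparators in those studies. The extra task payments in the app arm are a real difference between arms. But the plan still describes overall incentive amounts as similar, and it offers no argument for a difference near 50 points.

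**Conclusion.** The concern holds. The document gives 15 per condition in one place and 10 per arm in another, does not reconcile them, and attaches its only power figure to the larger number. If 10 per arm is correct, the effect that would give 90% gives about 65% to 75%, and less at very low or high abstinence rates. This assumes a two-sided 0.05 two-proportion test at one time point and lower-arm abstinence of 5% to 40%. The unstated effect size would, on its own, be only missing detail. The correction is worth making, but the feasibility conclusions do not depend on it.

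**What to change.** 1. State the planned and the achieved number per arm, and explain any difference.
2. Delete the 90% power sentence. Alternatively, restate it for the actual number per arm, with the assumed abstinence rates for app and office delivery and the test used.
3. Give the expected precision at the confirmed size. At 10 per arm the Newcombe 95% half-width for the difference in abstinence is about 0.32, 0.36 and 0.37 for rates near 10%, 30% and 50%.
4. When the pilot estimate is used to plan the larger study, report it with its confidence interval.

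This changes protocol and SAP wording only, with no extra participants or visits. The cost is a less favourable power figure if it is restated for 10 per arm.

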To quantitatively evaluate the *feasibility* and *acceptability* of Momba Live Long to postpartum women we will begin by calculating the number of women screened and eligible and enrolled. We will collect data on reasons women are not enrolled. We will consider a participation rate of $\geq 60\%$ for eligible women between screening and enrollment as supportive of feasibility. We will evaluate retention and set a threshold of 80% for the Momba Live Long group. Since feasibility also depends upon compliance to the challenges or office visits through which contingency management is delivered, we will use challenge completion and in-office visit attendance to assess compliance. Mixed-effects regression models will be conducted as outlined above for group comparisons. Because number of visits attended is a count variable, random effects regression with a negative binomial model will be used which is appropriate for count data.(45) Additional procedures to evaluate abstinence from smoking are described below.

Data Analysis for Pilot RCT: Descriptive statistics will summarize the data on all screened and randomized subjects. Baseline demographic and clinical characteristics for the randomized groups will be compared using chi-square tests for categorical variables and analysis of variance for continuous variables. All continuous variables will be examined for adherence to the normal distribution using normal probability plots and Kolmogorov-Smirnov tests. Dropouts and completers will also be compared on baseline characteristics using the same approach. Data analyses will be conducted using the intent-to-treat principle. We will use mixed-effects regression models to compare the two groups (Momba Live Long vs. in-office contingency management) using SAS PROC MIXED version 9.3. These models allow for different numbers of observations per subject, use all available data on each subject, and are unaffected by randomly missing data. They are flexible in modeling the correlation structure of the data. In each model, we will include fixed effects of time, group (Momba vs. in-office) and time by group, and random subject effects. If there are concerns of informative dropout and/or informative intermittent missing data, we will use pattern mixture models to perform sensitivity analyses to our main analyses.

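### The 90% power figure makes no allowance for dropout; at the plan's own 80% retention threshold it would be about 86%, or about 82% if the control arm is assumed to lose as many

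*Combined protocol and SAP*

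**What the plan says.** The power statement is in the last paragraph of Data Analysis for Pilot RCT. Its endpoint is given as "For the outcome of 7-day point prevalence for smoking abstinence at the end of the trial", and its terms are "15 subjects per condition, a 2-tailed alpha of .05 we will have power of 90" percent. It is conditional on "the same effect size found in other studies of contingency management with perinatal women smokers", but no abstinence rates or standardised effect are given. The same paragraph says that, as a pilot, the trial is not powered for its outcomes, and it cites guidance of 15-30 participants per cell.

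The feasibility part of the Proposed Analytic Plan says: "We will evaluate retention and set a threshold of 80% for the Momba Live Long group". It gives no time point for that threshold and no figure for the control arm.

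Data Analysis for Pilot RCT says the mixed-effects models "use all available data on each subject, and are unaffected by randomly missing data". If dropout may be informative, "we will use pattern mixture models to perform sensitivity analyses to our main analyses". The abstinence outcomes are named at two time points: the end of the trial and the 3-month follow-up.

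The Overview gives 10 women per arm and lists the attrition rate among the parameters the pilot will assess.

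**The concern.** The plan provides for dropout in its feasibility criteria, its comparison of dropouts with completers and its sensitivity analyses, but not in its power sentence. The trial could meet its own retention criterion and still have fewer than 15 assessed women in the Momba arm, so the 90% would not describe it.

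The mixed model does not make up the difference. Insensitivity to randomly missing data concerns bias; it does not restore lost information. The earliest named abstinence time point is the end of the trial, so a woman who leaves before then has no earlier outcome value from which the model could borrow.

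Little is at stake for the pilot itself, which disclaims power. What matters is that the one power figure in the document should be accurate on its own terms, since the plan offers the results as a basis for powering a larger study.

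**Working it through.** **Inputs from the document.** 15 per condition, two-sided alpha 0.05 and power 90% (Data Analysis for Pilot RCT); 80% retention threshold, Momba arm only (Proposed Analytic Plan); 10 per arm (Overview).

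**Assumptions.** The effect size is the one that gives exactly 90% at 15 v 15. Retention is read as the share with an end-of-trial assessment. Control-arm retention is either 100% or 80%, since the plan gives none.

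**The plan's own figure.** The 90% cannot be reproduced, because its effect size is not stated. It was therefore back-solved, held fixed, and power recomputed with fewer women.

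**Numbers assessed.** 0.80 × 15 = 12.

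**Arcsine effect size.** h = (1.960 + 1.2816) × √(2/15) = 1.184, and power = Φ(h × √[n₁n₂/(n₁+n₂)] − 1.960).

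- 15 v 15: 1.1836 × √7.5 − 1.960 = 1.282, power 90.0% (by construction)
- 12 v 15: 1.1836 × √6.667 − 1.960 = 1.096, power 86.3%
- 12 v 12: 1.1836 × √6 − 1.960 = 0.939, power 82.6%
- 10 v 10: 1.1836 × √5 − 1.960 = 0.687, power 75.4%

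**Pooled two-proportion formula.** Power = Φ([|p₂ − p₁| − 1.960 × SE₀] / SE₁), where SE₀ uses the pooled rate and SE₁ the separate rates. For each assumed control rate from 2% to 45%, the comparison rate was solved to give 90% at 15 v 15.

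Example, 0.20 v 0.752 (difference 0.552):

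- 15 v 15: SE₀ = √(2 × 0.476 × 0.524/15) = 0.182; SE₁ = √[(0.160 + 0.1865)/15] = 0.152; z = 1.28, power 90%
- 12 v 12: SE₀ = 0.204; SE₁ = 0.170; z = 0.897, power 81.5%
- 12 v 15: pooled rate 0.445; SE₀ = 0.192; SE₁ = 0.162; z = 1.08, power 86.0%

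**t-based version.** d = 1.226 was solved to give 90% at 15 v 15.

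| Women assessed (Momba v control) | Arcsine | Two-proportion, control rates 2-45% | t |
|---|---|---|---|
| 15 v 15 | 90% | 90% | 90% |
| 12 v 15 | 86.3% | 85.5-86.6% | 86.1% |
| 12 v 12 | 82.6% | 81.5% at every rate | 81.9% |
| 10 v 10, no loss | 75.4% | 73.1% at every rate | 73.7% |

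The fall from 90% thus depends little on the unstated effect size or on the choice among these formulas. All are approximations at small n, and none is the planned random effects logit model, so whole percentages are as fine as the result should be read.

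**The case against.** The strongest reply is that the plan says it is not powered, so finding less than 90% power tells the sponsor nothing new. That stands as to severity. It does not make the 90% accurate: the figure is in the same paragraph as the disclaimer, and the two already conflict.

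Second, 80% is a feasibility threshold rather than an expected dropout rate. It covers the Momba arm only and has no time point, so it need not mean 12 of 15 at the end of the trial. This also stands. A reader might infer that the protocol accepts 12 per condition and that 82% is its true power; the text supports no such figure for the control arm. On the plan's wording the nearer figure is about 86%.

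Third, 15 may mean women assessed rather than randomised. The sentence does not say. If assessed is meant, 80% retention in both arms would require 15/0.80 = 18.75, or 19 per arm. No such enrolment is stated, and the Overview's 10 per arm leaves no spare enrolment to support that reading. Either way a clarification is needed.

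Fourth, the 90% rests on a cited effect size that is not in the document. If power at 15 v 15 was rounded to 90%, or was higher, the other figures move with it.

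A reader might also infer a much larger loss by counting lost women as smoking. The plan has no such rule: it specifies models on all available data, with pattern mixture sensitivity analyses, and it gives no abstinence rates from which to size that scenario. Nor does the text show that the larger study would ignore dropout, since attrition rate is among the parameters to be assessed.

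**Conclusion.** The point holds in a limited form. The 90% carries no stated allowance for loss and does not hold at the retention the plan would count as success. If the effect gives exactly 90% at 15 v 15, and the 80% threshold is applied at the end of the trial, power falls by about 4 points when only the Momba arm loses women (about 86%) and by about 8 points if equal control-arm loss is assumed (about 82%).

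Severity is minor. The pilot disclaims power, and other features of the same sentence matter more: 15 per condition against 10 per arm in the Overview, and an effect size taken from contingency management studies although both arms here receive contingency management. At 10 per arm the same effect gives about 73-75% before any loss. The 86% and 82% figures therefore show the effect of dropout at the plan's stated 15; they do not estimate what this trial would achieve.

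**What to change.** Restate the power sentence along these lines:

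> The 90% applies to 15 women per condition with an end-of-trial assessment, if the effect size equals that found in other contingency management studies. At the 80% retention threshold it is about 86% (loss in the Momba arm only) or about 82% (equal loss assumed in both arms).

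In the same edit, say whether 15 means randomised or assessed, and reconcile the sentence with the statement that the pilot is not powered and with the 10 women per arm in the Overview. If 10 per arm is the intended size, the sentence has to be recast on that number, because 12 assessed per arm would exceed enrolment.

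The cost is a less favourable stated power and a short rewording. No added women, visits or staff are needed.

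### The 90% power figure borrows an effect of contingency management itself, but both arms receive contingency management, so it does not describe the app versus in-office comparison

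*Combined protocol and SAP*

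**What the plan says.** The power statement is in the section Data Analysis for Pilot RCT. It concerns end-of-trial abstinence ("For the outcome of 7-day point prevalence for smoking abstinence at the end of the trial"), assumes "15 subjects per condition, a 2-tailed alpha of .05", and claims "power of 90% if we have the same effect size found in other studies of contingency management with perinatal women smokers". No abstinence rates, effect measure or comparator are given for those other studies. They are identified only by a citation.

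Earlier in the same paragraph the plan says "Given that this is a pilot, we are not powered" to detect a significant difference on the outcomes.

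The Control Group section describes the comparator: "Control group mothers received traditional, in-office contingency management to prevent smoking relapse". On incentives it says "Financial incentives were delivered according to the same schedule at the same frequency as those delivered to mothers on Momba Live Long", and it calls the overall amounts similar. It names one exception: the app arm is also paid for completing tasks that promote abstinence. It then says of the aim that "we were not directly comparing the effectiveness of contingency management that has already been well established"; the question is delivery by smartphone against delivery in the office. The mixed models in Data Analysis for Pilot RCT use the same two-level group factor. There is no arm without CM.

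The Overview gives 10 women per arm.

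**The concern.** Power belongs to a particular contrast. The effect invoked is described as one found in studies of CM, and the Control Group section says that CM's effectiveness is not what this trial compares. Whatever benefit of CM the two arms share does not appear in their difference. What can appear is the effect of the app package (delivery route, the application itself, task payments) over and above office CM. The plan gives no reason to think this is as large as the effect of CM.

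Two internal conflicts add to this. A 90% figure sits in the same paragraph as a statement that the study is not powered, and it uses 15 per arm where the Overview gives 10.

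The stake is interpretation. If the app works just as well as office CM, a non-significant result is what should happen about 95% of the time or more. Beside a stated 90%, that result could be taken as failure of the app or as proof of equivalence, and neither would follow.

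**Working it through.** **Inputs from the plan.** n = 15 per arm, two-sided alpha 0.05, stated power 90%, binary endpoint (Data Analysis for Pilot RCT); n = 10 per arm (Overview). Abstinence rates and effect size are not stated, so every rate below is an assumption. A comparison of two proportions stands in for the planned random-effects logit model at one time point.

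**Step 1. Can the 90% be reproduced?** No. Without rates or an effect size it can be neither confirmed nor refuted. What can be found is the effect it implies.

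**Step 2. Effect implied by 90% at 15 per arm.** With the arcsine formula, h = (z₀.₉₇₅ + z₀.₉₀) × √(2/n) = (1.960 + 1.282) × √(2/15) = 1.184, where h = 2·arcsin√p₂ − 2·arcsin√p₁. Solving for p₂:

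| Assumed lower rate | Rate needed in the other arm | Difference (points) |
|---|---|---|
| 5% | 53% | 48 |
| 10% | 63% | 53 |
| 20% | 76% | 56 |
| 30% | 85% | 55 |
| 40% | 92% | 52 |
| 50% | 96% | 46 |

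Example: for p₁ = 30%, 2·arcsin√0.30 = 1.159; 1.159 + 1.184 = 2.343; sin²(2.343/2) = 0.85.

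The pooled normal approximation gives a similar range, about 48 to 55 points. Exact Fisher testing needs about 49 to 62.

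**Step 3. The same effect at 10 per arm.** Power = Φ(1.184 × √(10/2) − 1.960) = Φ(0.687) = 75%. The pooled approximation gives about 73%, and Fisher's test about 53% to 56%. So even on its own terms the 90% does not carry over to the arm size in the Overview.

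**Step 4. Power for smaller differences between two CM arms.** Exact power, summed over all pairs of binomial outcomes:

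| Assumed rates | n per arm | Pooled chi-square | Fisher |
|---|---|---|---|
| 40% vs 50% | 15 | 8% | 3% |
| 40% vs 60% | 15 | 18% | 10% |
| 40% vs 50% | 10 | 6% | 2% |
| 40% vs 60% | 10 | 13% | 5% |

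Over a wider assumed range (office CM 30% to 70%, app better by 5 to 20 points), the pooled approximation gives about 5% to 27% at 15 per arm, and Fisher about 2% to 15%.

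**Step 5. What the pilot can deliver.** At 40% against 60%, the half-width of a simple 95% interval for the difference is 1.96 × √[(0.4×0.6 + 0.6×0.4)/n]. This is 1.96 × √(0.48/15) = 0.35 at 15 per arm and 1.96 × √(0.48/10) = 0.43 at 10 per arm. An interval of ±35 to ±43 points shows plainly how little a non-significant result would settle.

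**The case against.** The strongest case for the plan has four parts.

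- **The sentence is conditional.** It says what power would be if the effect were that large. A reader might infer that the plan expects this effect, or that the 90% fixed the sample size. The text supports neither firmly: the stated basis for the number of women is a Stage 1b guideline of 15 to 30 per cell. Even so, a conditional power figure is useful only if its condition is relevant to the contrast, and no reason is given that it is.
- **The arms differ in more than delivery route.** A reader might infer that the design cannot show a difference of that size at all. That goes too far. The app arm is paid for extra tasks, and the shared benefit of CM drops out exactly only if the CM actually received is equal in both arms; the plan treats compliance as something to be measured. What stands is narrower: an effect of CM is not a justified assumption for this contrast.
- **The cited source is not available here.** That its comparator was no CM, or non-contingent payment, is inferred from the plan's description of a CM effect. If it compared two delivery routes, the plan should say so and give the rates.
- **Much of the remedy is already there.** The plan disclaims power and names the app versus office contrast. A reader might also infer that the larger study will be sized on the earlier CM effect; the documents do not say so. They base it on this trial's own results and commit to effect sizes and the direction of effects.

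These points lower the severity. They do not rescue the sentence, because the disclaimer contradicts the 90% and does not explain that the effect belongs to another comparison.

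**Conclusion.** The 90% figure is not supported for the comparison this trial makes. It is conditioned on an effect of CM, while both arms receive CM; it contradicts the disclaimer in its own paragraph; and it uses an arm size that differs from the Overview. Under assumed rates, it needs a gap of roughly 46 to 56 points between two groups that both receive CM. A 20-point gap would be detected 5% to 18% of the time, depending on test and arm size.

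The conclusion rests on the plan's own description of the borrowed effect as a CM effect. The percentages rest on assumed abstinence rates.

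Severity is moderate. The claim is conditional, low power is already admitted, the analytic goal is feasibility and acceptability, and Administration of Standardized Measures labels smoking prevalence a secondary outcome, although the Overview puts abstinence first.

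**What to change.** In Data Analysis for Pilot RCT:

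1. Delete the sentence claiming 90% power and keep the statement that the pilot is not powered.
2. State that the app minus in-office difference in 7-day abstinence will be reported with its 95% confidence interval, at the actual number of women per arm. Reconcile the 15 in this section with the 10 in the Overview.
3. Add one sentence saying that a non-significant difference will be read neither as failure of the app nor as equivalence to office CM.

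The change is to wording only. No procedure, treatment or analysis model changes. The one cost is that a favourable figure is withdrawn, which agrees with what the paragraph already says about power.
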